#### Tetriary (composite) estimand (continuous additional secondary endpoints)

The two continuous secondary additional endpoints 'Change from baseline to Week 16 in EASI score' and 'Change from baseline to Week 16 in Worst Daily Pruritus NRS (weekly average)' will be analysed as described for the two continuous secondary endpoints above, including the tipping point sensitivity analysis.

# 6.6.4 Multiple imputation

For the analysis of the primary and secondary endpoints, multiple imputation will be carried out as specified in the protocol, using SAS PROC MI. For multiple imputations related to the treatment policy estimand and the hypothetical estimand sensitivity analyses, the seed 11109925 will be used. The remaining seeds are specified in the protocol.

When performing mulitiple imputation of continuous parameter values, imputed values at visits prior to Week 16 outside the relevant parameter scale shall be used as is. Values imputed at Week 16 shall be truncated to the nearest upper or lower bound on the given scale. For example, negative imputed EASI values at Week 16 will be set to 0.

For imputation of IGA values, the LIKELIHOOD=AUGMENT option will be used (1).

For imputation of IGA values, it may occur that the observed data from which the imputation model is fitted does not contain all levels of the IGA predictors necessary for the imputation. For example, the imputation model for IGA values at Week 8 will be based on observed data from the subset of subjects with observed IGA values at both Week 6 and Week 8. If only the IGA values (0,1,2,3) are observed at Week 6 in this subset of subjects, the imputation model will not be able to predict IGA values at Week 8 for a subject with an IGA value of 4 at Week 6. To avoid this situation, in this specific example IGA values of 3 and 4 at Week 6 will be combined into a single category for the purpose of the imputation. In general, if this situation

Trial ID: LP0162-1325	Date: 20-May-2019	Version: 1.0
		Page 18 of 31

arises, IGA categories will be combined into a single category at the specific visit for the purpose of the specific imputation, according to the rules in Table 1.

IGA value(s) missing in imputation model	IGA categories combined
0	(0,1)
1	(0,1)
2	(2,3)
3	(2,3)
4	(3,4)

Table 1: Adjacent IGA categories combined in case of missing predictors in observed data

## 6.6.5 Secondary and other efficacy analysis

Reduction of Worst Daily Pruritus NRS weekly average of at least 4

The analyses will be based on subjects in the FAS with a baseline Pruritus NRS weekly average of at least 4.

The binary endpoint was to be analysed as described for the primary endpoint EASI75 using all three estimands. It is however expected that subjects will not fill in the eDiary when they have discontinued treatment, and it is considered likely, there will be no nominal Week 16 data available for discontinued subjects. If this is the case, the primary analysis of the tertiary estimand will not be estimated for this endpoint. The corresponding sensitivity analysis for the tertiary estimand, analysing subjects with missing Week 16 data as non-responders, while otherwise using observed data for the remaining subjects, will still be conducted.

#### Calculation of Weekly average of pruritus NRS

The weekly average will only be calculated if at least 4 assessment are available. When calculating the baseline value for the weekly average of Worst Daily Pruritus, the daily assessments in the 7 days preceding the randomisation will be used, including the day of randomisation.

For the initial treatment period, the NRS weekly average for Week 1 will be calculated based on scores recorded on day 1 to day 7 (where day 0 is the day of the first dose). Similarly, for Weeks 2 to Week 15, the weekly average for Week x will be calculated based on scores recorded on day 7\*x-6 to day 7\*x (where day 0 is the day of first dose). To account for the actual day maintenance or open-label treatment is initiated, the Week 16 weekly average will instead be based on the last 7 days before (and including) the day of the Week 16 visit, thus

Trial ID: LP0162-1325	Date: 20-May-2019	Version: 1.0
		Page 19 of 31

ensuring that the Week 16 weekly average is based on data from the initial treatment phase only, and also ensuring alignment in timing with other Week 16 efficacy endpoints. Also, for the calculation of Week 1 to Week 15 weekly averages, any scores recorded after the Week 16 visit date will be disregarded (only relevant if Week 16 visit is out of window).

For Week 17 of the maintenance treatment period, the weekly average will be based on the first 7 days after (not including) the Week 16 visit. For Week 18 to Week 52 of the maintenance treatment period, the weekly average for Week x will be calculated based on scores recorded on day 7\*x-6 to day 7\*x (where day 0 is the day of the first dose). Any scores recorded after initiation of open-label treatment will be disregarded.

#### PGI-B and PGI-S

For the PGI-B and PGI-S, which are not numerical, the worst score recorded during the week will be presented instead of weekly averages. The worst score will be derived if at least one measurement is available for the week in question. The same rules regarding visit windowing apply as for weekly average pruritus NRS described above. The daily scores will be presented graphically.

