- 9) The eDiary consists of (i) Eczema-related Sleep NRS, (ii) Worst Daily Pruritus NRS, (iii) Average Daily Pruritus NRS, (iv) PGI-B, and (v) PGI-S. The eDiary will be completed daily from Week -2 to Week 52.
- 10) IgE not assessed at screening.
- 11) Optional, selected trial sites only.
- 12) At baseline, a total of 4 skin biopsies will be taken (2 from lesional skin, 2 from non-lesional skin) at an anatomically similar site.

ADA, anti-drug antibodies; Bcg, background; BSA, body surface area; C-SSRS, Columbia-Suicide Severity Rating Scale; DLQI, Dermatology Life Quality Index; EASI, Eczema Area and Severity Index; EASI75, at least 75% reduction in EASI score; ECG, electrocardiogram; eDiary, electronic diary; EQ-5D-5L, EuroQoL 5-Dimension Health Questionnaire 5 Level; HADS, Hospital Anxiety and Depression Scale; IGA, Investigator's Global Assessment; IgE, immunoglobulin E; IMP, investigational medicinal product; NA, not applicable; NRS, numeric rating scale; PGI-B, Patient Global Impression of Bother; PGI-S, Patient Global Impression of Severity; POEM, Patient Oriented Eczema Measure; Q2W, every 2 weeks; SCORAD, Scoring Atopic Dermatitis; SF-36, 36-Item Short Form Health Survey; TSQM, Treatment Satisfaction Questionnaire for Medication; WPAI-GH, Work Productivity and Activity Impairment – General Health.

Trial ID: LP0162-1325	Date: 14-Aug-2018	Version: 4.0
		Page 22 of 169

Panel 3 Schedule of trial procedures: maintenance treatment period and follow-up

							N	Iainten	ance tı	eatmei	nt perio	bd							FU1 ²
Visit	13	14	15	16	17	18	19	20	21	22	23	24	25	26	27	28	29	30 ¹	31
Week	18	20	22	24	26	28	30	32	34	36	38	40	42	44	46	48	50	52	66
Visit window (days)	±3	±3	±3	±3	±3	±3	±3	±3	±3	±3	±3	±3	±3	±3	±3	±3	±3	±3	±3
Trial products (Section 9)																			
IMP administration and compliance	Х	X	Х	Х	Х	Х	Х	X	Х	Х	X	Х	Х	X	Х	Х	Х		
Concomitant medication/procedures	х	х	х	х	х	Х	х	x	х	х	x	х	х	x	Х	Х	х	х	х
Investigator assessments of efficacy (Sect	Investigator assessments of efficacy (Section 10.3.1)																		
IGA	X ³	X ³	X ³	X ³	X ³	X ³	X ³	X ³	X ³	X ³	X ³	X ³	X ³	X ³	X ³	X ³	X ³	Х	
EASI	X ³	X ³	X ³	X ³	X ³	X ³	X ³	X ³	X ³	X ³	X ³	X ³	X ³	X ³	X ³	X ³	X ³	х	
SCORAD		х		х		х		х		х		х		x		Х		х	
Subject assessments of efficacy (Section 1	10.3.2)																		
eDiary ⁴		<-==															>		
POEM and DLQI		х				Х				Х				x				Х	
EQ-5D-5L and HADS		х				х				х				x				х	
SF-36 and WPAI-GH		Х				Х				Х				X				Х	
TSQM				Х														х	

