10.3.2.4 Patient Global Impression of Bother

The Patient Global Impression of Bother (PGI-B) is a single item designed to capture the subject's perception of how bothered they have been by their AD over the past 24 hours at the time of completion. A 5-point categorical response scale will be used ('not at all', 'slightly', 'somewhat', 'a lot', 'very much'). Subjects will complete this item as part of the eDiary each day in the morning from Week -2 (visit 2) until Week 52. The PGI-B is included in the investigator trial file.

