10.3.2.5 Patient Global Impression of Severity

The Patient Global Impression of Severity (PGI-S) is a single item designed to capture the subject's perception of overall eczema symptom severity over the last 24 hours on a 4-point categorical response scale ('no symptoms' to 'severe'). Subjects will complete this item as

Trial ID: LP0162-1325	Date: 14-Aug-2018	Version: 4.0
		Page 72 of 169

part of the eDiary each day in the morning from Week -2 (visit 2) until Week 52. The PGI-S is included in the investigator trial file.

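### Weekly PGI-B and PGI-S are the worst score from as few as one diary entry, so sparse weeks look better on average in these descriptive tables

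*SAP*

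**What the plan says.** PGI-B and PGI-S are daily eDiary items. Protocol Section 4 (Panel 2, footnote 9) states: "The eDiary will be completed daily from Week -2 to Week 52". Each is an ordered scale. For PGI-B (Protocol 10.3.2.4), "A 5-point categorical response scale will be used". PGI-S (Protocol 10.3.2.5) has four categories.

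Under PGI-B and PGI-S, SAP 6.6.5 notes that the scales are not numerical, so "the worst score recorded during the week will be presented instead of weekly averages". The completeness rule is: "The worst score will be derived if at least one measurement is available for the week in question". The pruritus windowing rules are carried over, so a week holds at most seven entries, but the pruritus minimum is not carried over. That minimum, stated just above in the SAP, is: "The weekly average will only be calculated if at least 4 assessment are available". Nothing was found that adjusts for the number of entries. The same SAP paragraph adds: "The daily scores will be presented graphically".

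Protocol 12.3.5.4.2 makes the eDiary summaries descriptive. Its one treatment comparison for PGI-B is the number of days of no or slight bother, which does not use the weekly worst score.

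**The concern.** The average gets the stricter rule and the maximum the looser one. If days are missed at random, an average over fewer days is noisier but does not drift in either direction. A maximum does drift: dropping days can leave it unchanged or make it look better, never worse. The SAP's one-entry minimum therefore puts weeks resting on one entry and weeks resting on seven in the same table, as if they measured the same thing.

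At stake is how the weekly PGI tables are read. Diary collection runs to Week 52. If completion falls over that time, weekly worst scores would drift towards improvement with no change in symptoms. If completion differed between arms, part of any difference between them would be a completion effect.

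**Working it through.** The plan states no figure for these scores, so there is none to reproduce. The minimum entries (1 for PGI, 4 for pruritus), the seven-day week and the scale lengths come from the documents. Daily probabilities and within-week correlation are not given and are assumed below.

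**Step 1. Direction.** The maximum over a subset of days cannot exceed the maximum over all seven. In any one week the score changes only if every day at the worst level is missed. If all days score alike, nothing changes.

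**Step 2. Chance of missing the worst level.** Suppose k of 7 days are kept at random and m days are at the worst level. The chance that all m are missed is C(7−m, k) / C(7, k).

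| Days at worst level | 1 entry | 4 entries | 6 entries | 7 entries |
|---|---|---|---|---|
| m = 1 | 6/7 = 85.7% | 15/35 = 42.9% | 1/7 = 14.3% | 0% |
| m = 3 | 4/7 = 57.1% | 1/35 = 2.9% | 0% | 0% |

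The only assumption is that the kept days are random.

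**Step 3. Size in a worked example (assumed).** Let each day be bad with probability 0.20. With independent days, the chance that the week is scored bad from n entries is 1 − (1 − 0.20)^n:

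- 6 entries: 1 − 0.8^6 = 73.8%
- 4 entries: 1 − 0.8^4 = 59.0%
- gap: 14.8 points (14.7 before rounding)

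Daily ratings of a chronic disease in one subject are unlikely to be independent. The example was repeated with days sharing a common latent normal component of correlation rho:

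| rho | Bad week, 6 entries | Bad week, 4 entries | Gap (points) |
|---|---|---|---|
| 0 | 73.8% | 59.0% | 14.7 |
| 0.5 | 52.2% | 44.4% | 7.8 |
| 0.7 | 43.4% | 38.0% | 5.4 |
| 0.9 | 32.5% | 29.8% | 2.7 |

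**Step 4. What a 4-entry minimum would do (assumed).** Score PGI-B 0 to 4 with all five categories equally likely. The table gives the expected weekly worst score and its shortfall against a full week.

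| rho | 1 entry | 4 entries | 7 entries | Shortfall, 1 entry | Shortfall, 4 entries |
|---|---|---|---|---|---|
| 0 | 2.000 | 3.434 | 3.761 | 1.76 | 0.33 |
| 0.5 | 2.000 | 2.991 | 3.265 | 1.27 | 0.27 |
| 0.9 | 2.000 | 2.436 | 2.569 | 0.57 | 0.13 |

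The minimum removes most of the largest shortfall but not all of it. It would not alter the Step 3 gap, because both 4 and 6 entries satisfy it.

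**The case against.** The strongest reply is that nothing of consequence rests on this score. PGI-B and PGI-S are absent from the endpoint lists (Protocol Panels 6 and 7) and from both testing hierarchies (Protocol 12.3.4, SAP 6.6.1). In the PGI-B day count a skipped day cannot count as a good day, so skipping pulls the other way there. The daily scores are also plotted. All of this stands and limits the point to descriptive tables. A plot of daily scores does not, however, correct the weekly table.

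A second reply concerns bias between arms. A reader might infer that the plan builds in a spurious treatment difference of around 15 points. The documents do not support that. They give no completion rates by arm, the 6-versus-4 split is an illustration, and 15 points is the independent-days end of the range. The nearest statement is in SAP 6.6.5: "It is however expected that subjects will not fill in the eDiary when they have discontinued treatment". Once entries stop altogether, later weeks have no score at all; only the week in which they stop is partial. That statement therefore points mainly to missing weeks rather than sparse ones.

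A third reply is that the worst day is a legitimate thing to report, and that a weekly median describes a typical day instead. This also stands. Replacing the worst score with a median would be a preference, and a median of an even number of entries can fall between two categories.

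**Conclusion.** The point holds as a minor one. The weekly PGI-B and PGI-S worst scores depend on how many days were completed, and the SAP applies its weaker completeness rule to the statistic that needs the stronger one. The direction is certain: sparse weeks look equal or better, and better on average unless daily scores are constant. The size is not known. Under the assumptions shown, the 6-versus-4 gap runs from about 15 points (independent days) through 8 (correlation 0.5) to about 3 (correlation 0.9).

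Two stronger readings should be resisted. It does not follow that each skipped day improves the score; within a week that requires missing every day at the worst level. Nor does it follow that an efficacy conclusion is at risk, since no listed endpoint or planned treatment comparison uses the score.

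**What to change.** In SAP 6.6.5, under PGI-B and PGI-S, derive the weekly worst score only when at least 4 of the 7 daily entries are available, matching the pruritus NRS rule. Because that reduces the dependence without removing it, also present the proportion of completed days in each category, by week and arm. This proportion has no one-way drift with the number of entries when days are missed at random. It would still be affected if subjects skip days because of how they feel. The worst score can stay alongside it.

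The cost is a wording change and one extra derivation. Some sparse weeks become missing in the worst-score table.

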#### Percentage change in EASI score, initial treatment period

In addition to the repeated measurements analysis of absolute reduction in EASI score during the initial treatment period which was planned in the protocol, the same analysis will be conducted for the percentage change from baseline in EASI scores during the initial treatment period.

#### Subgroup analyses

To access the consistency in response rate across subgroup the following subgroup analyses will be performed for the primary estimand:

- IGA 0/1 by baseline IGA
- IGA 0/1 by region
- EASI75 by baseline IGA
- EASI75 by region

#### Efficacy analyses open-label period

For the open-label treatment period IGA, EASI75, EASI and SCORAD will be summarised by visit and initial treatment for subjects who transferred to open-label treatment at Week 16,

Trial ID: LP0162-1325	Date: 20-May-2019	Version: 1.0
		Page 20 of 31

and by week since transfer to open-label and at Week 52, by previous maintenance treatment for subjects who transferred to open-label treatment after Week 16. IGA, EASI and SCORAD for subject who transferred to open-label treatment at Week 16 and IGA for subject who transferred to open-label treatment after Week 16 will be presented in figures.

Trial ID: LP0162-1325	Date: 20-May-2019	Version: 1.0
		Page 21 of 31

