7.2 Number of subjects needed

Assuming a screening failure rate of 25%, approximately 1040 subjects will be screened and approximately 780 subjects will be randomly assigned to trial treatment in the initial treatment period (3:1; 585 subjects in the tralokinumab arm and 195 subjects in the placebo arm). At Week 16, approximately 40% of the tralokinumab treated subjects are expected to be re-randomised (2:2:1 to tralokinumab Q2W, tralokinumab Q4W, and placebo, respectively) into the maintenance treatment period; any subject who does not achieve a clinical response at Week 16 will be treated with open-label tralokinumab Q2W.

The statistical power considerations for this sample size (n=780) are described in Section 12.1.

This trial will be conducted at approximately 130 sites in Europe, North America, and Japan. The anticipated minimum number of subjects per trial site is 4 and the maximum number of subjects is 30.

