8.5 Discontinuation

A subject may withdraw from trial or from treatment at any time (prior to first dose or during treatment period) at his/her own request. A subject may be withdrawn at any time at the discretion of the investigator. Discontinued subjects will not be replaced.

Medical reasons for permanent discontinuation of IMP are given in Section 9.8.1.

Assessments

Subjects who permanently discontinue IMP for any reason will be asked to attend an early termination visit and return to the trial site for 1 or 2 additional visits as indicated below depending on the time of discontinuation of IMP (see the SoP [Section 4] for data to be collected at these visits). The investigator will review any AEs which will be followed-up according to Section 11.6, if the subject agrees.

Subjects who permanently discontinue IMP prior to Week 16 will be asked to attend:

- Early termination visit.
- Nominal Week 16 visit (16 weeks after randomisation).
- Safety follow-up visit (16 weeks after last administration of IMP).

Subjects who permanently discontinue IMP at Week 16 or after Week 16 will be asked to attend:

- Early termination visit.
- Safety follow-up visit (16 weeks after last administration of IMP).

If a subject withdraws from the trial, he/she may request destruction of any samples taken and not tested, and the investigator must document this in the site's trial records.

Reason(s) for discontinuation from IMP and withdrawal from the trial must be recorded in the medical records and the eCRF (lack of efficacy, AE, withdrawal by subject, lost to follow-up, death, other). For subjects randomised to IMP but not attending any post-baseline visits, it will be recorded whether any safety evaluations were performed after exposure to IMP.

Lost to follow-up

A subject will be considered lost to follow-up if they repeatedly fail to return for scheduled visits and if the trial site is not able to get in contact with the subject.

The following actions must be taken if a subject fails to return to the trial site for a required visit:

- The trial site must attempt to contact the subject and reschedule the missed visit as soon as possible and counsel the subject on the importance of maintaining the assigned visit schedule and ascertain whether or not the subject wishes to and/or should continue in the trial.

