9.8 Dose modification and IMP discontinuation rules

9.8.1 Reasons for permanent discontinuation of IMP

Subjects will be permanently discontinued from IMP in the event of:

- Anaphylactic reaction or other severe systemic reaction to IMP injection.
- An AE that, in the opinion of the investigator or sponsor's medical expert, contraindicates further dosing.
- Diagnosis of a malignancy during the trial, excluding carcinoma in situ of the cervix, or localised squamous or basal cell carcinoma of the skin.
- Evidence of pregnancy.
- Any infection that is opportunistic, such as active tuberculosis and other infections whose nature or course may suggest an immuno-compromised status.
- Severe laboratory abnormalities:
 - ALT and/or AST values >3x ULN with total bilirubin >2x ULN (unless elevated bilirubin is related to Gilbert-Meulengracht Syndrome)
 - Confirmed AST and/or ALT >5x ULN (for more than 2 weeks)

Subjects in open-label treatment (tralokinumab 300 mg Q2W with optional use of TCS) who in the opinion of the subject or investigator have unacceptable treatment effect of tralokinumab may discontinue open-label treatment and enter the safety follow-up period.

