12.3.6 Analysis of maintenance treatment

12.3.6.1 Analysis of maintenance endpoints

For the two dichotomous maintenance endpoints, IGA 0/1 and EASI75 at Week 52, an adapted version of the primary estimand for the primary endpoints will be considered:

• Treatment difference in response rates of IGA 0/1 and EASI75 after 52 weeks achieved without rescue medication and without transfer to open-label treatment

The adapted estimand takes into account that throughout the maintenance period subjects will be actively discontinued from the treatment randomised at Week 16 and transferred to the open-label tralokinumab arm if they meet the prespecified treatment failure criteria described in Section 7.1.

This estimand assesses the expected difference in response rates (defined as response obtained without initiation of any rescue medication and without transfer to open-label treatment) after 52 weeks in patients responding to tralokinumab at Week 16 (as measured by a positive IGA 0/1 or EASI75 response), resulting from a maintenance treatment regimen with tralokinumab Q2W or tralokinumab Q4W compared to a treatment regimen with placebo.

Primary analysis for the maintenance estimand

All subjects who prior to the Week 52 visit have received rescue medication, including TCS, and/or been transferred to the open-label tralokinumab arm will be considered non-responders.

This reflects an assumption that initiation of rescue medication or transfer to open-label treatment indicates failure of the re-randomised treatment assigned at Week 16, and that a (possible) observed positive response thereafter is not attributable to the treatment received from Week 16. In addition, all subjects with missing endpoint data at Week 52 visit will be imputed as non-responders.

Trial ID: LP0162-1325	Date: 14-Aug-2018	Version: 4.0
		Page 109 of 169

The 4 hypotheses of primary interest for maintenance treatment will be tested sequentially with the next hypothesis in the sequence only being tested if the previous one was significant. The multiple testing procedure planned to control the overall type 1 error rate for the trial is described in detail in Section 12.3.4. The maintenance endpoints will be evaluated in the following order:

- No difference between Q2W and placebo for IGA 0/1 at Week 52.
- No difference between Q2W and placebo for EASI75 at Week 52.
- No difference between Q4W and placebo for IGA 0/1 at Week 52.
- No difference between Q4W and placebo for EASI75 at Week 52.

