12.3.10 General principles

Unless otherwise stated, all significance tests will be two-sided using the 5% significance level. All CIs will be presented with 95% degree of confidence.

An observed-cases approach will be used for tabulations of data by visit (i.e. involving only those subjects who attended each specific visit).

Trial ID: LP0162-1325	Date: 14-Aug-2018	Version: 4.0
		Page 114 of 169

Categorical data will be summarised using the number and percentage of subjects in each category and treatment group. Continuous data will be summarised using the mean, median, standard deviation, minimum and maximum values.

All the analyses specified in the protocol will be reviewed in relation to the blinded data actually obtained and the statistical analysis plan update will be finalised before breaking the randomisation code.

Any changes from the statistical analysis planned in this clinical trial protocol will be described and justified in a protocol amendment, the statistical analysis plan update and/or in the CTR dependent on the type of deviation.

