# 6.8.6 Early termination and unscheduled visits

When no data is available from a certain scheduled post-baseline visit for a particular subject, data from early termination visits and unscheduled visits have the potential to replace data from that particular scheduled visit in data summaries, provided the data is collected between 6 days before and 7 days after the planned time point for the scheduled visit, as displayed below.

Visit (Target day)	Visit window (Day is date of assessment
	minus date of first dose)
Week 2 (Day 14)	Day 8 to 21
Week x (Day $7*x$ ) (where $x=4, 6,, 52$ )	Day 7*x-6 to 7*x+7
Week x (Day 7*x) (where x=54, 56,, 68)	Day 7*x-6 to 7*x+7
(only applicable for subjects enrolled in	
short-term extension)	
Safety follow-up	106-119 days after last dose

When both unscheduled and early termination visits exist within the given visit window, the early termination visit will be selected for analysis. When no early termination visits and several unscheduled visits exist, the unscheduled visit closest to the target day will be selected for analysis. If the difference is a tie, the latest unscheduled visit will be selected.

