# 6.8.7 Handling of Drop-outs and Missing Values

Missing values will be handled as described in the Clinical Trial Protocol.

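### The descriptive Week 52 open-label response uses observed cases only, although subjects may leave open-label treatment for poor effect, so it is likely to overstate response among those who entered

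*SAP*

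**What the plan says.** For subjects who transfer at Week 16, the SAP (section 6.6.5, Efficacy analyses open-label period) says: "For the open-label treatment period IGA, EASI75, EASI and SCORAD will be summarised by visit and initial treatment". For those who transfer later, the summary is by time since transfer and at Week 52, split by previous maintenance treatment. Neither part states a denominator.

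Missing data are covered only by reference. SAP section 6.8.7 says: "Missing values will be handled as described in the Clinical Trial Protocol". The applicable protocol rule is in section 12.3.10: "An observed-cases approach will be used for tabulations of data by visit (i.e. involving only those subjects who attended each specific visit".

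Three other provisions decide who is still observed at Week 52:

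- **Exit.** Under protocol section 9.8.1, open-label subjects who in their own or the investigator's view "have unacceptable treatment effect of tralokinumab may discontinue open-label treatment and enter the safety follow-up period".
- **Visits after exit.** Protocol section 8.5 begins "Subjects who permanently discontinue IMP at Week 16 or after Week 16 will be asked to attend" and lists an early termination visit and a safety follow-up visit. Only subjects who stop before Week 16 get a nominal visit at the endpoint time. Panel 4 schedules no IGA, EASI or SCORAD at follow-up.
- **Use of early termination data.** Under SAP section 6.8.6 such a value can stand in for a scheduled visit "provided the data is collected between 6 days before and 7 days after the planned time point for the scheduled visit".

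For the maintenance endpoints the protocol takes the other approach (section 12.3.6.1): "all subjects with missing endpoint data at Week 52 visit will be imputed as non-responders".

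**The concern.** A subject who enters open-label treatment at Week 16 and stops at, say, Week 28 for poor effect is absent from both numerator and denominator at Week 52. One permitted reason for leaving is the outcome being tabulated. The table then describes subjects still under assessment, while a reader is likely to want the share of all entrants who responded.

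Week 16 transfers start with neither IGA 0/1 nor EASI75, so a rising response rate will be read as late response to continued tralokinumab with optional TCS. Part of that rise could come from failures leaving the denominator. The trial report would also show Week 52 IGA 0/1 and EASI75 on two bases: missing as non-response for maintenance, observed cases for open-label. The two could easily be compared as if they were alike.

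**Working it through.** **1. Who has a Week 52 value.** The Week 52 window in SAP section 6.8.6 runs from 7 × 52 − 6 = Day 358 to 7 × 52 + 7 = Day 371. An early termination or unscheduled assessment outside it does not count for Week 52.

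**2. Planned size of the group.** The documents state no open-label number, so it is built from the planning figures.

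- Arms (protocol section 7.2): "585 subjects in the tralokinumab arm and 195 subjects in the placebo arm".
- About 40% of tralokinumab subjects are expected to be re-randomised (section 7.2). Check: 0.40 × 585 = 234, against the 235 EASI75 responders stated in section 12.1.
- The placebo EASI75 rate of 15% (section 12.1) is taken as the placebo clinical response rate. This is an approximation, since clinical response also includes IGA 0/1.

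Transfers at Week 16 = 0.60 × 585 + 0.85 × 195 = 351 + 165.75 ≈ 517, and 517/780 = 66%.

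- Placebo response of 10%: (351 + 175.5)/780 = 67.5%. At 25%: (351 + 146.25)/780 = 63.75%.
- If 5% of those randomised (39) are lost from this group before Week 16: (517 − 39)/780 = 61%. If 10% (78): (517 − 78)/780 = 56%. These losses are assumed.

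**3. Size of the excess.** Let q be the response among those assessed at Week 52, d the fraction of entrants without a Week 52 assessment, and r the response those subjects would have shown.

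- Response among all entrants = q(1 − d) + r·d.
- Excess of the observed-case figure = d(q − r).

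The documents give none of q, d or r. With r = 0, the response among all entrants is:

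| d | q = 40% | q = 50% | q = 60% |
|---|---|---|---|
| 5% | 38.0% | 47.5% | 57.0% |
| 10% | 36.0% | 45.0% | 54.0% |
| 15% | 34.0% | 42.5% | 51.0% |
| 20% | 32.0% | 40.0% | 48.0% |
| 30% | 28.0% | 35.0% | 42.0% |

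The excess over this grid depends on r:

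- r = 0: from 0.05 × 40 = 2 points to 0.30 × 60 = 18 points.
- r = q/2: half of that, 1 to 9 points.
- r = q: zero.

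**The case against.** The strongest reply is that the method is pre-specified and the tables are only descriptive. Open-label efficacy is not an endpoint in Panels 6 or 7, lies outside both testing hierarchies, and has no hypothesis or comparison. Non-response imputation in section 12.3.6.1 belongs to a confirmatory randomised comparison, and the protocol uses multiple imputation and LOCF elsewhere. Reasons for stopping, including lack of efficacy, are tabulated for the open-label set by last visit (sections 8.5 and 12.3.1), so attrition is disclosed. All of this stands and limits the weight of the point. The disposition table does not, however, put leavers back into the response denominator.

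The documents do not support several stronger readings that a reader might infer:

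- *No missing-data rule applies.* One does: observed cases, through section 12.3.10.
- *These are the only efficacy results for these subjects.* Week 16 non-responders are in all initial-period analyses. Later transfers count as failures in the maintenance analysis and generally as events in time to relapse. Only results after transfer depend on these tables.
- *The columns would become comparable once missing data are handled.* Week 16 transfers are selected by outcome within each arm, so the columns are not randomised comparisons under any rule.
- *A fixed denominator should apply at every visit.* For later transfers, who may enter at any visit from Week 22, this fails. A subject transferring at Week 44 cannot reach 12 weeks since transfer by Week 52, and counting that as non-response would deflate the rate for administrative reasons.

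**Conclusion.** The point holds as a cheap improvement to descriptive tables. The stated rules remove subjects who leave for poor effect from the Week 52 open-label response, so overstatement relative to all entrants is the likely direction.

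That the rate *is* overstated is tempting to infer but is not shown. It requires leavers to respond less often than stayers, and departures for adverse events or personal reasons need not push the rate upward. The 2 to 18 point range is the case in which no leaver responds, over assumed values of d and q. The range of 1 to 9 points and the value of zero show how far it depends on r. The two-thirds share likewise rests on planning rates and no loss before Week 16.

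**What to change.** In SAP section 6.6.5, keep the observed-case tables and add beside them IGA 0/1 and EASI75 at Week 52 with all subjects who entered open-label treatment as the denominator, counting a missing Week 52 value as non-response. Present Week 16 transfers by initial arm. Present later transfers by previous maintenance arm, at Week 52 only and not by week since transfer. Show n at every visit in tables and figures.

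Optionally, add a Week 52 EASI and SCORAD summary that uses the early termination value for subjects who stopped; Panel 4, footnote 1, already has it collected.

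The cost is SAP wording and a few descriptive tables. No new data are needed, since the cut-off is the last subject's Week 52 visit (protocol section 12.3.9). The downside is lower reported open-label rates. Counting missing as non-response is also conservative for exits unrelated to efficacy, which is why both versions should be shown.
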